3.2.8 Exclusion Criteria

3.2.8.1 Patients unable to swallow whole tablets.

3.2.8.2 Patients who in the opinion of the investigator are not able to comply with the study procedures are not eligible.

3.2.8.3 Prior Therapy

- Patients who have received prior therapy with axitinib, nivolumab, or other PD1/PD-L1 targeted therapies.
- Patients who have received prior therapy with more than one anti-VEGF based agent (antibody or tyrosine kinase inhibitor).
- Patients with hypersensitivity to axitinib, nivolumab, or any of its excipients.
- Patients who previously received an allogeneic stem cell transplant (SCT) or solid organ transplant are not eligible.
- Patients may not be receiving any other investigational agents (within 4 weeks prior to study enrollment).
- Patients who have received prior anti-cancer monoclonal antibody (mAb) within 4 weeks prior to study enrollment or who have not recovered (i.e., \leq Grade 1 or at baseline) from adverse events due to agents administered more than 4 weeks prior to enrollment.
- Surgery: Patients who have had or who are planning to have the following invasive procedures are not eligible:
 - o Major surgical procedure, laparoscopic procedure, open biopsy, core biopsy, fine needle aspirate, or significant traumatic injury within 7 days prior to enrollment. **NOTE:** External central lines must be placed at least 3 days prior to

planned treatment initiation and subcutaneous ports must be placed at least 7 days prior to planned treatment initiation.

- Patients who are planning cytoreductive surgery within the first 12 weeks following therapy initiation.
- Patients who have a serious or non-healing wound or ulcer at the time of study enrollment are not eligible.
- Patients who have a history of abdominal fistula, gastrointestinal perforation, or intra-abdominal abscess within 28 days of study enrollment are not eligible.
- Patients who have received prior targeted small molecule therapy within 2 weeks of enrollment or have not recovered (i.e., \leq Grade 1 or at baseline) from adverse events due to agents administered more than 4 weeks prior to enrollment. **NOTE:** Subjects with \leq Grade 2 neuropathy are an exception to this criterion and may qualify for the study.

3.2.8.4 Pre-existing conditions, which may include:

- Additional known malignancy that is progressing or requires active treatment. Exceptions include basal cell carcinoma of the skin, or squamous cell carcinoma of the skin that has undergone potentially curative therapy, or *in situ* cervical cancer.
- Patients with underlying immune deficiency, chronic infections including hepatitis, tuberculosis (TB), or autoimmune disease.
- HIV-infected patients with the exception of patients on an effective anti-retroviral therapy with an undetectable viral load within 6 months prior to enrollment.
- Patients with underlying hematologic issues including congenital bleeding diathesis, known previous GI bleeding requiring intervention within the past 6 months, history of hemoptysis within 42 days prior to study enrollment, active pulmonary emboli, or deep vein thromboses (DVT) that are not stable on anticoagulation regimen.
- Patients must not have had significant vascular disease (i.e. Moya-Moya, aortic aneurysm requiring surgical repair).
- A known history of, or any evidence of active, non-infectious pneumonitis.
- Patients with known active central nervous system (CNS) metastases and/or carcinomatous meningitis or leptomeningeal disease. Patients with previously treated brain metastases may participate provided they are stable (without evidence of progression by imaging for at least 4 weeks prior to study enrollment and any neurologic symptoms have returned to baseline), have no evidence of new or enlarging brain metastases, and are not using steroids for at least 7 days prior to study enrollment. This exception does not include carcinomatous meningitis which is excluded regardless of clinical stability.
- Any uncontrolled, intercurrent illness including but not limited to ongoing or active infection, symptomatic congestive heart failure, unstable angina pectoris, cardiac arrhythmia.

- Any serious medical or psychiatric illness/condition including substance use disorders likely in the judgment of the Investigator(s) to interfere or limit compliance with study requirements/treatment.
- Patients with active autoimmune disease that has required systemic treatment in the past 2 years (i.e. with use of disease modifying agents, corticosteroids or immunosuppressive drugs). Replacement therapy (e.g., thyroxine, insulin, or physiologic corticosteroid replacement therapy for adrenal or pituitary insufficiency, etc.) is not considered a form of systemic treatment.

3.2.8.5 Treatments and/or medications the patient is receiving or has received that would make her/him ineligible, including:

- Concomitant (or receipt of) treatment with medications that may affect the metabolism of nivolumab and/or axitinib within 7 days prior to planned first dose of protocol therapy.
- A live vaccine within 30 days of planned first dose of protocol therapy. **NOTE:** Inactivated flu vaccines are allowed; however intranasal influenza vaccines (e.g., Flu-Mist®) are live attenuated vaccines, and are not allowed.

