3.2.6 Prior Therapy

Patients must have fully recovered from the acute toxic effects of all prior chemotherapy, immunotherapy, or radiotherapy prior to entering this study.

- a. Myelosuppressive chemotherapy: Must not have received within 2 weeks of entry onto this study (6 weeks if prior nitrosourea).
- b. Immunotherapy: Must not have received within 4 weeks of entry onto this study.
- c. Biologic (anti-neoplastic agent): At least 7 days since the completion of therapy with a biologic agent.
- d. Radiation therapy (RT): ≥ 2 weeks for local palliative RT (small port); ≥ 6 months must have elapsed if prior craniospinal RT or if $\geq 50\%$

radiation of pelvis; ≥ 6 weeks must have elapsed if other substantial BM radiation.

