3.2.7 Organ Function Requirements

3.2.7.1 Adequate Bone Marrow Function Defined As:

- Peripheral absolute neutrophil count (ANC) $\geq 1000/\mu\text{L}$
- Platelet count $\geq 75,000/\mu\text{L}$ (transfusion independent)
- Hemoglobin $\geq 8.0 \text{ g/dL}$ (may receive RBC transfusions)

3.2.7.2 Adequate Renal Function Defined As:

- Urine protein: $\leq 30 \text{ mg/dL}$ in urinalysis or $\leq 1+$ on dipstick, unless quantitative protein is $< 1000 \text{ mg}$ in a 24 h urine sample.
- **For patients < 18 years of age:** Serum creatinine $\leq 1.5 \times$ upper limit of normal (ULN), or measured or calculated* creatinine clearance or radioisotope GFR $\geq 60 \text{ mL/min}/1.73 \text{ m}^2$ for patient with creatinine levels $> 1.5 \times$ institutional ULN, or a serum creatinine based on age/gender as follows:

Age	Maximum Serum Creatinine (mg/dL)	
	Male	Female
1 to < 2 years	0.6	0.6
2 to < 6 years	0.8	0.8
6 to < 10 years	1	1
10 to < 13 years	1.2	1.2
13 to < 16 years	1.5	1.4
≥ 16 years	1.7	1.4

The threshold creatinine values in this table were derived from the Schwartz formula for estimating GFR utilizing child length and stature data published by the CDC.⁶¹

- **For patients ≥ 18 years of age:** Serum creatinine $\leq 2 \times$ ULN, or measured or calculated* creatinine clearance or radioisotope GFR $\geq 40 \text{ mL/min}/1.73 \text{ m}^2$ for patient with creatinine levels $> 2 \times$ institutional ULN.

*Creatinine clearance should be calculated per institutional standard.

3.2.7.3 Adequate Liver Function Defined As:

- Serum total bilirubin $\leq 1.5 \times$ ULN for age, or direct bilirubin \leq ULN for patients with total bilirubin levels $> 1.5 \times$ ULN.
- SGOT (AST) or SGPT (ALT) $< 3 \times$ ULN for age.
- Albumin $> 2.5 \text{ mg/dL}$.

3.2.7.4 Adequate Cardiac Function Defined As:

- Shortening fraction of $\geq 27\%$ by echocardiogram, or
- Ejection fraction of $\geq 50\%$ by radionuclide angiogram.
- No history of myocardial infarction, severe or unstable angina, or peripheral vascular disease.
- QTc ≤ 480 msec. Note: Patients with Grade 1 prolonged QTc (450-480 msec) at the time of study enrollment should have

correctable causes of prolonged QTc addressed if possible (i.e., electrolytes, medications).

3.2.7.5 Adequate Coagulation Function Defined As:

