- International Normalized Ratio (INR) or Prothrombin Time (PT) $\leq 1.5 \times$ ULN. However, if patient is receiving anticoagulant therapy, PT or PTT should be within therapeutic range of intended use of anticoagulants.
- Activated Partial Thromboplastin Time (aPTT) $\leq 1.5 \times$ ULN unless patient is receiving anticoagulant therapy as long as PT or PTT is within therapeutic range of intended use of anticoagulants.

3.2.7.6 Adequate Blood Pressure Control Defined As:

- A baseline blood pressure (BP) \leq the 95th percentile for age, height, and gender for patients < 18 years old (see [Appendix III](#)), or ≤ 150 mmHg (systolic) and ≤ 90 mmHg (diastolic) for patients ≥ 18 years old.

Note: 2 serial blood pressures should be taken at least 1 hour apart and averaged to determine baseline BP (see [Section 5.2.5.1](#)).

- Patients are eligible if on stable doses (≥ 7 days) of anti-hypertensive medications with a baseline BP meeting the criteria above.

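### Minor: the small-molecule exclusion in Section 3.2.8.3 leaves days 15 to 28 after the last TKI dose without a recovery test

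*Combined protocol and SAP*

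**What the plan says.** The targeted small-molecule bullet in Section 3.2.8.3 has two parts. It excludes "Patients who have received prior targeted small molecule therapy within 2 weeks of enrollment or have not recovered" (to Grade 1 or lower, or to baseline) "from adverse events due to agents administered more than 4 weeks prior to enrollment". A note exempts neuropathy up to Grade 2 and nothing else.

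The antibody bullet in the same section excludes "Patients who have received prior anti-cancer monoclonal antibody (mAb) within 4 weeks prior to study enrollment or who have not recovered" and continues with the same recovery wording, so its two periods are both 4 weeks.

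Section 3.2.6 adds a general rule: "Patients must have fully recovered from the acute toxic effects of all prior chemotherapy, immunotherapy, or radiotherapy prior to entering this study". It has no time window, and it does not name targeted small molecules.

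One prior anti-VEGF agent, antibody or TKI, has been allowed since Amendment 2A (Sections 2.1.3 and 3.2.8.3). Section 3.2 says that the criteria are to be read literally and may not be waived. Section 3.1.5 requires the projected treatment start to fall within 5 calendar days of enrollment.

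**The concern.** A recovery rule should be at least as strict soon after a drug is stopped as it is later. Read by last dose, this one is stricter at 5 weeks than at 3, and the protocol gives no reason. The exemption for Grade 2 neuropathy alone suggests that other Grade 2 symptoms were meant to be screened. At cross-over, Section 4.1 lets axitinib be added only after recovery from relevant toxicity, again with no time window.

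At stake are consistency between sites and a small safety margin. Two sites reading the criteria literally could decide the same patient differently. A patient with residual symptoms from one VEGFR TKI could start another within days. The toxicities overlap: Section 6.1 lists diarrhea, fatigue and palmar-plantar erythrodysesthesia as likely (over 20%) with axitinib, and the last was one of the two DLTs in the pediatric phase 1 study (Section 2.3). Some DLT definitions include persistent Grade 2 events (Sections 5.1.2.6 and 5.1.2.9). These depend on attribution to protocol therapy, which carry-over makes harder to judge.

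**Working it through.** The plan gives no figure of its own on this point, so none is reproduced.

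**Interval check, in days from last TKI dose to enrollment**

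| Days | Small-molecule bullet | Antibody bullet |
|---|---|---|
| 0–14 | excluded by washout | excluded by washout |
| 15–28 | neither part applies | excluded by washout |
| 29 and later | recovery test applies | recovery test applies |

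The uncovered interval is 28 − 14 = 14 days. With at most 5 days from enrollment to treatment, the first axitinib dose falls between day 15 and day 28 + 5 = 33 after the last TKI dose.

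If *administered* means any dose, a TKI begun more than 28 days before enrollment is covered even if it stopped on day 20. Only a course given wholly within days 15–28 then escapes, which is about 0 patients. Item c of Section 3.2.6 counts from completion of therapy; this bullet does not specify the starting point.

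**What other criteria already catch**

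- Section 3.2.7 sets limits for counts, kidney function, proteinuria, cardiac function and QTc, and has items titled "Adequate Liver Function Defined As" and "Adequate Blood Pressure Control Defined As".
- Section 3.2.8.3 also covers wounds ("Patients who have a serious or non-healing wound or ulcer at the time of study enrollment are not eligible"), fistula and perforation.
- Section 3.2.8.4 covers bleeding ("known previous GI bleeding requiring intervention within the past 6 months, history of hemoptysis within 42 days prior to study enrollment"), thrombosis and pneumonitis.

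What remains is mainly Grade 2 symptomatic toxicity. The pre-treatment re-check in Section 3.2 lists laboratory tests only. The general axitinib hold in Section 5.2.4 begins at Grade 3. Below that, Section 5.2.2 offers only discretionary breaks of up to 7 days per cycle.

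**Number of patients, last-dose reading**

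Inputs from the documents:
- Maximum still to enroll: 2 per month × 14 months = 28 (Section 9.1).
- If the trial stops at the futility look with a true HR of 1.0: 24 per year is 2 per month, and 2 × 9 months = 18 (Section 9.2).
- Allocation to Arm A: 1/2 (Section 9.2).

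Assumptions, not in the documents:
- 20–40% have had a prior TKI.
- 30–60% of those enroll 15–28 days after the last dose.
- 10–30% of those have residual Grade 2 symptoms.

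Formula: patients affected = number enrolled × the three proportions; multiply by 1/2 for those starting axitinib.

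- Low: 18 × 0.20 = 3.6; × 0.30 = 1.08; × 0.10 = 0.11; × 1/2 = 0.05 on axitinib.
- High: 28 × 0.40 = 11.2; × 0.60 = 6.7; × 0.30 = 2.0; × 1/2 = 1.0 on axitinib.

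**The case against.** The strongest reply is that the gap depends on a word the bullet does not contain. It refers to agents administered, not last administered. TKIs are usually taken continuously, so under a literal reading most would count as given more than 4 weeks before enrollment. That reading is possible, and it would remove almost all of the effect. But it also makes the 4-week limit nearly pointless, and the text does not state it.

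Second, Section 3.2.6 may already cover the case. The banking text (Section 15.2.3 and its subsections) uses chemotherapy loosely for treatment on this trial, which consists only of axitinib and nivolumab. Item a of Section 3.2.6 needs the qualifier myelosuppressive, which can be taken to imply a wider class. This is a fair argument for intent, but the term is undefined and TKIs are not named.

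Third, the protocol tolerates Grade 2 toxicity on treatment: axitinib may restart at Grade 2 (Section 5.2.4), and dose titration is barred only by reactions above Grade 2 (Section 4.3.3). This stands as a limit on the safety argument. It does not explain why recovery is tested at 5 weeks and not at 3.

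Fourth, the criteria to start each cycle point to Section 5.0 for ongoing toxicity, and a physical exam precedes each cycle. For symptoms of Grade 3 or higher this points to holding axitinib. For Grade 2 symptoms the general hold rule does not act.

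**Conclusion.** The concern holds and is minor. The two periods in the small-molecule bullet do not meet, and the bullet leaves open whether the gap is 14 days or practically nothing. On the last-dose reading, roughly 0.1 to 2.0 patients are affected, 0.05 to 1.0 of them on axitinib. On the any-dose reading the number is near 0. These figures rest on the three assumed proportions and on Section 3.2.6 screening out nobody, so they are best read as an order of magnitude.

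The consequences are limited. Baseline findings are to be recorded with term and grade when possible (Section 11.4.1), which gives DLT attribution a reference. One patient alone cannot breach the limit of 3 DLTs in the first 10 treated (Section 9.5). Unchanged Grade 2 carry-over stays off the on-treatment adverse event form (Appendix I) and outside the Grade 3 or higher non-hematologic and Grade 4–5 events that Section 9.3 analyzes. The primary analysis and its operating characteristics do not change.

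**What to change.** In the small-molecule bullet of Section 3.2.8.3, make the recovery test apply to *any previously administered agent, regardless of time since last dose*. Alternatively, replace 4 weeks with 2 weeks in the recovery part only. Either change reduces the uncovered interval from 14 days to 0 and makes the choice between last dose and any dose immaterial. Keep the Grade 1 or baseline standard and the Grade 2 neuropathy exception.

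The cost is a few words of eligibility text in the next amendment, and an occasional patient who must wait for toxicity to resolve before enrolling.

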3.2.8.6 Pregnancy and Breast Feeding

3.2.8.6.1 Due to risks of fetal and teratogenic adverse events as seen in animal studies, a negative pregnancy test must be obtained in females of childbearing potential, defined as females who are post-menarchal. If the urine test is positive or cannot be confirmed as negative, a serum pregnancy test will be required.

3.2.8.6.2 Females of childbearing potential that are sexually active must agree to either practice 2 medically accepted highly-effective methods of contraception at the same time or abstain from heterosexual intercourse from the time of signing the informed consent through 5 months after the last dose of study drug.

3.2.8.6.3 Lactating females are not eligible unless they have agreed not to breastfeed their infants starting with the first dose of study therapy through 5 months after the last dose of study therapy.

3.2.8.7 Male patients of reproductive potential must agree to use an adequate method of contraception starting with the first dose of study therapy through 7 months after the last dose of study therapy. Prior history of vasectomy does not replace requirement for contraceptive use.

3.2.9 Regulatory Requirements

3.2.9.1 All patients and/or their parents or legal guardians must sign a written informed consent.

3.2.9.2 All institutional, FDA, and NCI requirements for human studies must be met.

4.0 TREATMENT PROGRAM

Timing of protocol therapy administration, response assessment studies, and surgical interventions are based on schedules derived from the experimental design or on established standards of care. Minor unavoidable departures (up to 72 hours) from protocol directed therapy and/or disease evaluations (and up to 1 week for surgery) for valid clinical, patient and family logistical, or facility, procedure and/or anesthesia scheduling issues are acceptable (except where explicitly prohibited within the protocol).

4.1 Overview of Treatment Plan

Prior to Amendment 2A, the study was a randomized three-arm phase 2 study evaluating the clinical benefit of axitinib, nivolumab, and their use in combination for the treatment of tRCC.

As of Amendment 2A, Arm B (axitinib alone) is permanently closed to accrual, and prospective patients will be randomly assigned to one of the following arms:

Arm A: Axitinib + Nivolumab

Arm C: Nivolumab

As of Amendment 5A, patients who are initially randomized to Arm C (nivolumab alone) and experience progressive disease prior to Cycle 22 will be permitted to crossover to Arm A (axitinib + nivolumab). For patients who crossover to Arm A, they are to continue on their current nivolumab schedule and start axitinib as soon as it is made available. NOTE: Patients must use the NCI supplied drug. Commercially supplied axitinib is not allowed.

Axitinib will be administered at a starting dose of 5 mg PO BID for patients \geq 18 years of age, and at 2.4 mg/m²/dose (maximum of 5 mg/dose) PO BID for patients $<$ 18 years of age. See [Appendix IV](#) for axitinib dosing nomogram. Individual patient dose titration of axitinib (escalation from starting dose) is permitted on protocol therapy, at the discretion of the treating physician. Refer to [Section 4.3.3](#) or [4.4.3](#) for dose titration criteria.

Nivolumab will be given at either 240 mg IV every 2 weeks or 480 mg IV every 4 weeks for patients \geq 18 years of age, and at 3 mg/kg IV (maximum of 240 mg/dose) every 2 weeks for patients $<$ 18 years of age. Pre-medication is not required as infusion reactions are rare, but anaphylactic precautions should be observed during each infusion of nivolumab. If \geq Grade 2 infusion reaction occurs, the infusion should be stopped and supportive care given as per institutional guidelines. See [Section 5.3](#) for management and dose modification guidelines for infusion reactions. Investigators are advised to monitor for fever, chills, shakes, itching, rash, hypertension or hypotension, or difficulty breathing during and immediately after administration of nivolumab.

Combination therapy will be given with agents at full single agent doses as above.

Each cycle of therapy will be 4 weeks. Tumor disease evaluation will occur after Cycles 2, 4, 6, 9, 12, and then every 4 cycles thereafter, or at any time clinical progression is suspected. If pseudoprogression is suspected (until any degree of response is observed), disease evaluation must occur after every cycle ([Section 10.2.1](#)). Absent disease

progression or unacceptable toxicity, patients may continue on protocol therapy for up to 2 years duration or completion of 26 cycles, whichever comes first. Disease evaluations (including imaging) will continue during follow-up according to the schedule outlined in [Section 7.2](#).

For patients who progress on Arm C prior to Cycle 22, cross-over to Arm A is permitted. Patients should resume Arm A therapy as soon as PD is identified. Nivolumab should continue uninterrupted according to the previously established schedule for that patient (either every 2 or 4 weeks). Axitinib should be added as soon as it becomes available from NCI and the patient has recovered from any relevant toxicity. Subsequent disease evaluations should occur as above timed from the first cycle of combination therapy. The first cycle of combination therapy after cross-over will be defined as the cycle for which > 14 days of axitinib is given, with Day 1 of Cycle 1 after cross-over defined as the day of first nivolumab dose during that cycle after axitinib is started or on the day axitinib is started if given concurrently. **NOTE:** The total protocol therapy received on AREN1721 (whether delivered on Arm A, Arm C, or Arm C+A) is not to exceed 26 cycles or 2 years, whichever comes first.

NOTE:

- Patients who have not had cytoreductive nephrectomy prior to trial enrollment but who elect to have cytoreductive nephrectomy during therapy may remain on protocol therapy.
- Cytoreductive therapy is not permitted in the first 12 weeks after starting protocol therapy.
- Axitinib must be held for 7 days before and after surgery. See [Section 13.1.2](#) for more details.

For COG Supportive Care Guidelines see:

<https://childrensoncologygroup.org/index.php/cog-supportive-care-guidelines>.

